# 10.2 Independent Data Monitoring Committee (DMC)

An independent DMC will be constituted for this study to monitor important aspects of study conduct, including safety results on an ongoing basis. The DMC will consist of 3 members who will be selected by the Sponsor but will be independent from the Sponsor. The clinicians on the committee will not participate in the study as Principal or Co-investigators, and should be isolated from the study if their institution is a study site. The DMC members receive no financial incentives for their participation, but are reimbursed only for customary consultative and administrative support fees.

DMC meeting frequency and conduct is outlined in a separate DMC Charter. An independent unblinded statistician will provide the committee with masked data for review

(treatment A versus treatment B), but will not be a member of the committee. All members of the DMC will treat study data, reports, meeting discussions, and conclusions as confidential.

#### 11 IEC/IRB APPROVAL

The Principal Investigator agrees to provide the Independent Ethics Committee (IEC)/Institutional Review Board (IRB) with all appropriate material, including a copy of the informed consent. The study will not be initiated until the Investigator obtains written approval of the research plan (protocol) and the informed consent document from the appropriate IEC/IRB and copies of these documents are received by Nabriva Therapeutics AG.

It is the Investigator's responsibility to obtain IEC/IRB approval for all subsequent major changes to the protocol, in compliance with local law. Appropriate reports on the progress of this study will be made by the Investigator to the IEC/IRB and Sponsor in accordance with applicable government regulations and in agreement with policy established by the Sponsor.

#### 12 ETHICAL CONDUCT OF THE STUDY

This clinical study will be conducted in compliance with this Protocol, the guidelines of the World Medical Association Declaration of Helsinki in its revised edition (Fortaleza, Brazil, October 2013), the guidelines of International Conference on Harmonization (ICH) Good Clinical Practice (GCP) (CPMP/ICH/135/95), European Union (EU) Clinical Trials Directive 2001/20/EC, EU Commission Directive 2005/28/EC, and Code of Federal Regulation (CFR) Title 21, CFR Part 50, 56 and 312, designated Standard Operating Procedures, and with local laws and regulations relevant to the use of new therapeutic agents in the country of conduct.

#### 13 INFORMED CONSENT

The International Conference on Harmonization (ICH) has issued guidelines to provide protection for human subjects in clinical investigations. The ICH Tripartite Guideline for Good Clinical Practice establishes the general requirements for informed consent.

A properly executed, written informed consent in compliance with the terms of these guidelines shall be obtained from each subject before entering the study, or before performing any unusual or non-routine procedure in relation to the study. The purpose of the study, procedures to be carried out, and potential hazards will be described to each potential subjects in non-technical terms. Subjects (or their legally authorized representative) will be required to read, voluntarily sign, and date an informed consent form summarizing the discussion at Screening, and will be assured that they may withdraw from the study at any time without jeopardizing their medical care.

Subjects (or their legally authorized representative) will sign and date 1 copy of the informed consent form which will be photocopied. In accordance with local regulations, the original and copies of the signed and dated consent may be retained by the subject (or their legally authorized representative) and/or retained on file by the Investigator, as applicable.

The consent form must be approved by the appropriate IEC/IRB and Sponsor before study initiation at a study site. Any subsequent changes to the approved informed consent form must be reviewed and approved by the appropriate IEC/IRB and Sponsor before implementation.

#### 14 QUALITY ASSURANCE AND QUALITY CONTROL

Standard Operating Procedures belonging to Nabriva Therapeutic AG or designee(s) will be adhered to for all activities relevant to the quality of the study and are routinely monitored by the Quality Assurance (QA) Division.

Data will undergo quality control checks prior to clinical database lock. Sponsor-designated, independent monitors will be responsible for the monitoring of the study and its data within the eCRFs.

A QA audit of this study may be conducted by the Sponsor or Sponsor's designee. The QA auditor will have access to all medical records, the Investigator's study-related files and correspondence, information in the informed consent documentation of this study, and study drug storage facilities.

An inspection of this study may be conducted by a regulatory agency. The Investigator agrees to contact the Sponsor as soon as possible, but not later than within 1 week, upon notification of an inspection by a regulatory agency. The Investigator agrees to allow the Inspector direct access to all relevant documents and to allocate his/her time and that of study personnel to the Inspector to discuss findings in any relevant issues. The Investigator will allow Sponsor personnel to be present as an observer during a regulatory inspection, if requested.

#### 15 DATA HANDLING AND RECORD KEEPING

#### 15.1 Data Handling

Data will be recorded at sites using eCRFs and reviewed by the Sponsor or designee during monitoring visits. The recorded data in the EDC system will be verified with source documents. All corrections or changes made to any study data must be appropriately tracked in an audit trail in the EDC system. eCRFs will be considered complete when all missing, incorrect, and/or inconsistent data has been accounted for. Data collected at baseline will only be entered into the eCRF if the subject is eligible for study participation following review of the data by the Investigator or designee.

Adverse events, concomitant medication data and clinical observations will be in the subjects' hospital notes, or recorded on source data forms, and will be transferred into the eCRF after assessment by the Investigator or designee.

Data produced by automatic devices with original print-outs (e.g., clinical laboratory test results, ECG traces, BP measurements) will be included in the source documentation. Clinical laboratory parameters are to be reviewed, signed and dated by the Investigator or

designee. Any results outside the normal range should be designated by the Investigator or designee as not clinically significant (NCS) or clinically significant (CS).

#### 15.2 Subject Confidentiality

Investigator and his/her staff will be required to manage subject data collected for the study in accordance with applicable laws and regulations on personal data protection.

**US:** All US-based investigational sites and laboratories or entities providing support for this study, must, where applicable, comply with the Health Insurance Portability and Accountability Act (HIPAA) of 1996. An investigational site that is not a Covered Entity as defined by HIPAA must provide documentation of this fact to Nabriva Therapeutics AG.

EU: Data collected during this study may be used to support the development, registration or marketing of lefamulin. Nabriva Therapeutics AG will control all data collected during the study, and will abide by the EU Directive on Data Privacy concerning the processing and use of subjects' personal data. For the purpose of data privacy legislation, Nabriva Therapeutics AG will be the data controller.

After subjects have consented to take part in the study their medical records and the data collected during the study will be reviewed by Nabriva Therapeutics AG or its representatives. These records and data may, in addition, be reviewed by the following: independent auditors who validate the data on behalf of Nabriva Therapeutics AG; third parties with whom Nabriva Therapeutics AG may develop, register or market lefamulin; national or local regulatory authorities and the IRB/IECs that gave approval for this study to proceed.

Subjects will be known by a unique number; however, their date of birth can also be collected if not in contradiction with any requirements (e.g., from IECs) and used to assist Nabriva Therapeutics AG to verify the accuracy of the data, for example, that the laboratory results are assigned to the correct subject. The results of this study may be recorded and transferred to and used in other countries throughout the world, which may not afford the same level of protection that applies within the EU. The purpose of any such transfer would be to support regulatory submissions in other countries.

# 15.3 Computer Systems

Data will be processed using a validated computer system conforming to regulatory requirements.

# 15.4 Data Entry

Data must be recorded using the EDC system as the study is in progress. All study personnel must log into the system using their secure user name and password in order to enter, review, or correct study data. These procedures must comply with the Title 21 Code of Federal Regulations (21 CFR Part 11) for US sites and EU Directives 2001/20/EC and 2005/28/EC for EU sites. All passwords will be strictly confidential.

#### 15.5 Data Validation

Validation checks programmed within the EDC system as well as supplemental validation performed via review of the downloaded data will be applied to the data in order to ensure accurate, consistent, and reliable data. Data identified as erroneous, or data that are missing, will be referred to the investigative site for resolution through data queries.

eCRFs must be reviewed and electronically signed by the Investigator who signed the protocol.

#### 15.6 Record Keeping

Raw data generated in connection with this study as well as an original copy of the final clinical study report, will be retained in archive until at least 5 years after the last approval of a marketing application in an ICH region and until there are no pending or contemplated marketing applications in an ICH region or at least 5 years have elapsed since the formal discontinuation of clinical development of lefamulin. These documents will be retained for a longer period if required by the applicable regulatory requirements or by an agreement with the Sponsor. It is the responsibility of the Sponsor to inform the Investigator/Institution as to when these documents no longer need to be retained.

As required under European Directive 2005/28/EC, Article 17, all 'essential documents' (as described in the ICH GCP Guidelines) must be retained by Nabriva Therapeutics AG and the Investigator for at least 5 years after the completion of the clinical study. Therefore all studies, independent of where they were conducted in the world, must follow this requirement in the event a submission is ever made in the EU. These documents may be retained for a longer period, however, if required by the applicable regulatory requirements or by an agreement with Nabriva Therapeutics AG. It is the responsibility of Nabriva Therapeutics AG to inform the Investigator as to when these documents no longer need to be retained. The Investigator must obtain written permission from Nabriva Therapeutics AG prior to the destruction of any study document.

The retention of investigator study records is an investigator responsibility and Nabriva Therapeutics AG will neither arrange nor pay for this activity. Any transfer of ownership of the content of the clinical trial master file is the responsibility of the investigator or site representative, and shall be documented. The new owner shall assume the responsibilities set forth in the applicable regulations.

These records must be made available at reasonable times for inspection and duplication, if required, by a properly authorized representative of the US Food and Drug Administration (FDA) in accordance with 21 CFR 312.68 or other national or foreign Regulatory Authorities in accordance with regulatory requirements.

#### 16 TERMINATION OF STUDY

The Sponsor reserves the right to discontinue this study at any time.

#### 17 FINANCING AND INSURANCE

The costs necessary to perform the study will be agreed with each Investigator and will be documented in a separate financial agreement that will be signed by the Investigator and Nabriva Therapeutics AG (or designee), prior to the start of the study. A statement regarding insurance/indemnity such as Association of British Pharmaceutical Industry (ABPI) should also be included.

The Investigator will be required to disclose any financial arrangement whereby the value of the compensation for conducting the study could be influenced by the results or outcome of the study. The following information will be collected: any significant payments of other sorts from Nabriva Therapeutics AG, (e.g., money to fund ongoing research, compensation in the form of equipment, retainer for ongoing consultation or honoraria); any proprietary interest in lefamulin; any significant equity interest in Nabriva Therapeutics AG as defined in 21 CFR 54 2(b).

In consideration of participation in the study, Nabriva Therapeutics AG will pay the Investigator or nominated payee the sums set out in the payment schedule attached to the Investigator agreement.

#### 18 PUBLICATION POLICY

It is intended that the results of the study may be published as scientific literature. Results may also be used in submissions to Regulatory Authorities. The following conditions are to protect commercial confidential materials (e.g., patents, etc.), not to restrict publication.

All information concerning lefamulin (such as patent applications, formulae, manufacturing processes, basic scientific data, or formulation information supplied to the Investigator by Nabriva Therapeutics AG and not previously published) is considered confidential by Nabriva Therapeutics AG and shall remain the sole property of Nabriva Therapeutics AG. The Investigator agrees not to use it for other purposes without Nabriva Therapeutics AG written consent.

It is understood by the Investigator that Nabriva Therapeutics AG will use the information developed in this clinical study in connection with the development of lefamulin and, therefore, may be disclosed as required to other Nabriva Therapeutics AG Investigators or any appropriate international Regulatory Authorities. In order to allow for the use of information derived from this clinical study, the Investigator understands that he/she has an obligation to provide Nabriva Therapeutics AG with complete test results and all data developed during this study.

All manuscripts, abstracts or other modes of presentation arising from the results of the study must be reviewed and approved in writing by Nabriva Therapeutics AG in advance of submission. The review is aimed at protecting Nabriva Therapeutics AG's proprietary information existing either at the date of the commencement of the study or generated during the study.

The detailed obligations regarding the publication of any data shall be set out in the agreement between each Investigator and Nabriva Therapeutics AG.

# **20 APPENDICES**

Appendix 1	Clinical Laboratory Tests (Safety)
Appendix 2	Short Acting Antibiotics
Appendix 3	Closely Monitored CYP3A4 Substrates and P-Glycoprotein Substrates (excluding strong CY3A inducers and inhibitors and excluding strong P-glycoprotein inhibitors)
Appendix 4	Prohibited Strong P-Glycoprotein Inhibitors and Strong CYP3A Inducers and Inhibitors
Appendix 5	Drugs That Prolong QT

# **Appendix 1** Clinical Laboratory Tests (Safety)

Blood and urine samples for the following laboratory tests will be sent to a central laboratory for testing.

#### Hematology

Complete blood count (CBC) with RBC indices and WBC differential

Platelet count

#### Chemistry

**BUN** 

Creatinine

Glucose

Sodium

Potassium

Chloride

Calcium

Magnesium

Phosphorus

AST

ALT

**GGT** 

Alkaline Phosphatase

**CPK** 

Total Bilirubin

Direct Bilirubin

Uric Acid

Albumin

**Total Protein** 

#### Urinalysis

Specific gravity

pH, glucose, protein, blood, ketones, bilirubin and leukocyte esterase by dipstick Microscopic examination (all samples)

#### Other tests

Procalcitonin

#### **Testing at Screening Only**

Serum pregnancy test

Urine pregnancy test (testing kit provided by central laboratory; test to be performed at the local site prior to randomization)

# Appendix 2 Short Acting versus Long Acting Antibiotics

Short-acting	Long-acting	
Cephalosporins		
Cefaclor, Cefadroxil, Cefdinir, Cefepime, Cefixime (200 mg), Cefotaxime, Cefpodoxime, Cefprozil, Ceftazadime, Ceftibuten, Cefditoren, Cefruoxime, Cephalexin, Loracarbef	Cefixime (400 mg), Ceftriaxone	
Fluoroqu	iinolones	
Ciprofloxacin, Norfloxacin	Gatifloxacin, Gemifloxacin, Grepafloxacin, Levofloxacin, Moxifloxacin, Sparfloxacin	
Macrolides and Ketolides		
Clarithromycin, Erythromycin, Roxithromycin	Azithromycin, Clarithromycin XL (extended release), Dirithromycin, Telithromycin	
Penicillins and Carbapenems		
Amoxicillin, Amoxicillin-Clavulanate, Amoxicillin-Sulbactam, Ampicillin, Ampicillin- Sulbactam, Dicloxacillin, Imipenem, Meropenem, Nafcillin, Oxacillin, Penicillin-G, Penicillin-V, Piperacillin, Piperacillin- Tazobactam, Ticaracillin-Clavulanate	Ertapenem, Penicillin-G, Benzathine/Procaine	
Tetracyclines		
Doxycycline (100 mg), Minocycline, Tetracycline	Doxycycline (200 mg), Minocycline Extended Release	

# Appendix 3 Closely Monitored CYP3A4 Substrates and P-Glycoprotein Substrates (excluding strong CY3A inducers and inhibitors and excluding strong P-glycoprotein inhibitors)

Closely Monitored CYP3A4 Substrates		
Alfentanyl	Domperidone	Pimozide
Alprazolam	Eplerenone	Progesterone
Amiodipine	Estradiol	Propranolol
Aprepitant	Fentanyl	Quetiapine
Aripiprazole	Finasteride	Quinine
Astemizole	Gleevec	Reserpine
Buspirone	Haloperidol	Salmeterol
Cafergot	Hydrocortisone	Sildenafil
Caffeine	Lercanidipine	Sirolimus
Chlorpheniramine	Lidocaine	Terfenadine
Cilostazol	Methadone	Testosterone
Cocaine	Midazolam	Trazodone
Codeine	Nateglinide	Triazolam
Dapsone	Nifedipine	Zaleplon
Dexamethasone	Nisoldipine	Ziprasidone
Dextromethorphan	Nitrendipine	Zolpidem
Docetaxel	Ondansetron	

Closely Monitored P-Glycoprotein Substrates		
Apixaban	Fexofenadine	Ranitidine
Carvedilol	Fosamprenavir	Rivaroxaban
Cimetidine	Ivermectin	Saxagliptin
Colchicine	Ledipasvir	Silodosin
Dabigatran	Loperamide	Sitagliptin
Daclatasvir	Losartan	Sofosbuvir
Dasabuvir	Maraviroc	Tetracycline
Dexamethasone	Methylprednisolone	Tipranavir
Digoxin	Methotrexate	Tolvaptan
Domperidone	Morphine	Umeclidinium
Edoxaban	Ombitasvir	Vecuronium
Empagliflozin	Paliperidone	Vilanterol
Estradiol	Paritaprevir	
Ezetimibe	Prazosin	

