## **AMENDMENT 2: 17-MAR-2016**

Amendment 2 addresses an inconsistency within the protocol. In accordance with Appendix 4 to the protocol, the use of strong P-glycoprotein inhibitors during study participation is prohibited. Thus, progesterone-containing products (such as oral contraceptives) are prohibited. In addition to revising the inclusion criterion associated with use of oral contraceptives, wording was added to the prohibited medications section for emphasis. These changes were made to the study synopsis, as applicable. Added text is **bolded**; deleted text is **struck through**.

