- Receipt within 7 days before enrollment of Class IA or Class III anti-arrhythmic medication or, in the opinion of the Investigator, subject may require such medication during the study. (Class 1A: Quinidine, Procainamide, Disopyramide; Class III: Amiodarone, Dofetilide, Ibutilide, Sotalol)
- Receipt within 7 days before enrollment of medication that has the potential of prolonging the QT interval or, in the opinion of the Investigator, subject may require such medication during the study (see Appendix 5).
- 8. Be receiving a strong p-glycoprotein inhibitor or a strong CYP3A inducer or inhibitor (see Appendix 4).
- 9. Have a history of tendon disease/disorder, myasthenia gravis, or known or suspected central nervous system (CNS) disorders (severe cerebrovascular arteriosclerosis, epilepsy, or other risk factors that may predispose to seizures).
- 10. Have a history of any hypersensitivity or allergic reaction to any fluoroquinolone, or any drug in the pleuromutilin class (i.e., retapamulin).
- 11. Have severely impaired renal function, defined as estimated creatinine clearance (CrCl) ≤30 mL/min as calculated by the Cockcroft-Gault formula.
- 12. Have evidence of significant hepatic, hematologic, or immunologic disease including any of the following:
  - Known acute hepatitis, including acute viral hepatitis.
  - Aspartate aminotransferase (AST) or alanine aminotransferase (ALT) level > 5 times the upper limit of normal (ULN),
  - Total bilirubin > 3 times the ULN (unless known Gilbert's disease).
  - Aspartate aminotransferase (AST) or alanine aminotransferase (ALT) level > 3 times the upper limit of normal (ULN) and total bilirubin > 2 times the ULN.
  - History of cirrhosis of the liver.
  - Manifestation of end-stage liver disease, such as ascites or hepatic encephalopathy.
  - Current or anticipated neutropenia (<500 neutrophils/mm^3).
  - Thrombocytopenia (<50,000 platelets/mm^3).
  - Known infection with human immunodeficiency virus and a CD4 count < 200/mm^3.
- 13. Have known severe immunosuppression, including but not limited to receipt of corticosteroid therapy (≥20 mg of prednisone/day or equivalent for >4 weeks) within the previous 8 weeks; solid organ or bone marrow transplantation within the previous 12 months; or currently receiving cytotoxic chemotherapy.

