#### 6.8.2 Concomitant Medication

All concomitant medications taken during the study will be recorded in the subject's eCRF.

In the case that additional antibiotic treatment is required for the current episode of CABP, the subject's study drug will be discontinued and they will be considered to have an IACR of

Failure; however, subjects will continue to be followed for safety as detailed in Section 6.18.1.

Other systemic antibacterial agents that are potentially effective against pathogens associated with CABP should not be administered during the study except in the case of CABP treatment failure or when medically necessary for treatment of a concomitant infection. The following antibacterial agents are permitted:

- Anti-tuberculosis drugs isoniazid, ethambutol and pyrazinamide
- Cinoxacin
- Dapsone
- Enoxacin
- Fidaxomicin
- Methenamine Mandelate
- Metronidazole
- Naladixic Acid
- Nitrofurantoin
- Norfloxacin
- Oral Vancomycin

Although all drugs that are metabolized by CYP3A4 are not prohibited, they should only be used when necessary and with appropriate subject monitoring. *In vitro* studies demonstrated that lefamulin may inhibit the metabolism of substrates of CYP3A4; however, results obtained from Phase 1 drug interaction studies performed demonstrate that lefamulin has a marginal effect on CYP3A4 inhibition in humans and no change in lefamulin's dose is required. In addition, all drugs that are P-glycoprotein substrates are not prohibited; however, they should only be used when necessary and with appropriate subject monitoring. A list of drugs that are CYP3A4 substrates and P-glycoprotein substrates is provided in Appendix 3.

Close monitoring is recommended in subjects who require medication that can reduce potassium levels (e.g., loop and thiazide-type diuretics, laxatives and enemas [high doses], corticosteroids, amphotericin B) or medication that is associated with clinically significant bradycardia.

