# Appendix 4 Prohibited Strong P-Glycoprotein Inhibitors and Strong CYP3A Inducers and Inhibitors

Prohibited Strong P-Glycoprotein Inhibitors		
Amiodarone	Indinavir	Ranolazine
Atorvastatin	Itraconazole	Reserpine
Boceprevir	Ketoconazole	Ritonavir
Bromocriptine	Linagliptin	Saquinavir
Captopril	Lopinavir and ritonavir	Simeprevir
Carvedilol	Lovastatin	Simvastatin
Cobicistat	Meperidine	Suvorexant
Conivaptan	Methadone	Tacrolimus
Cyclosporine	Nelfinavir	Tamoxifen
Diltiazem	Nicardipine	Telaprevir
Doxazosin	Pentazocine	Ticagrelor
Dronedarone	Progesterone	Verapamil
Felodipine	Quercetin	
Fluvastatin	Quinidine	

Prohibited Strong CYP3A Inhibitors	Prohibited Strong CYP3A Inducers
Indinavir	Efavirenz
Nelfinavir	Nevirapine
Ritonavir	Phenobarbital
Itraconazole	Phenytoin
Ketoconazole	Pioglitazone
Nefazodone	Rifabutin
Saquinavir	Rifampin
Suboxone	St. John's Wort
Carbamazepine	Troglitazone

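### Appendix 3 lists four drugs for monitored use that Appendix 4 prohibits, contrary to Appendix 3's own heading

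*Protocol*

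**What the plan says.** Protocol Section 6.8.2 covers substrates in two sentences. For CYP3A4: "Although all drugs that are metabolized by CYP3A4 are not prohibited, they should only be used when necessary and with appropriate subject monitoring". For P-glycoprotein: "all drugs that are P-glycoprotein substrates are not prohibited; however, they should only be used when necessary and with appropriate subject monitoring". It then directs the reader to the list: "A list of drugs that are CYP3A4 substrates and P-glycoprotein substrates is provided in Appendix 3". It makes no exception for drugs that are also in Appendix 4 or Appendix 5.

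The heading of Appendix 3 does make an exception: "Closely Monitored CYP3A4 Substrates and P-Glycoprotein Substrates (excluding strong CY3A inducers and inhibitors and excluding strong P-glycoprotein inhibitors").

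Appendix 4 is titled "Prohibited Strong P-Glycoprotein Inhibitors and Strong CYP3A Inducers and Inhibitors". Two provisions rely on it. Exclusion criterion 8 in Section 4.2 says a subject must not "Be receiving a strong p-glycoprotein inhibitor or a strong CYP3A inducer or inhibitor (see Appendix 4"). Section 6.9 prohibits strong P-glycoprotein inhibitors by reference to Appendix 4 and adds a note against progesterone-containing contraceptives.

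QT-prolonging drugs are handled separately. Section 6.9 prohibits them and exclusion criterion 7 excludes on them. Both cite Appendix 5, which says that its list is not exhaustive.

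Amendment 2 bears on the same subject. Its rationale opens "Amendment 2 addresses an inconsistency within the protocol" and continues "In accordance with Appendix 4 to the protocol, the use of strong P-glycoprotein inhibitors during study participation is prohibited". It applied that ban to progesterone-containing products by changing inclusion criterion 8 and Section 6.9.

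**The concern.** A drug cannot be both a prohibited strong P-glycoprotein inhibitor and an entry in a list whose heading excludes such inhibitors. If Appendix 3 contains Appendix 4 drugs, a site that goes from Section 6.8.2 to Appendix 3 would conclude that they are usable with monitoring, while a site that goes from Section 6.9 to Appendix 4 would conclude that they are banned. The risk is greatest for a drug considered after randomization, because exclusion criterion 8 is framed around what the subject is receiving at entry.

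The prohibition has a pharmacological context. Section 1.4 identifies lefamulin as a P-glycoprotein substrate, and Section 1.5.3 reports QT prolongation that depends on peak concentration. A site misled by Appendix 3 could give a drug that the sponsor chose to ban, or commit an avoidable protocol deviation.

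**Working it through.** The plan gives no figure to reproduce. The check compares the names printed in Appendices 3, 4 and 5 of the Protocol, by exact match followed by a search for close spellings.

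**Inputs (counts of printed entries)**

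- Appendix 3: 50 CYP3A4 substrates + 40 P-glycoprotein substrates = 90 entries. Dexamethasone, domperidone and estradiol are in both tables, so 90 − 3 = 87 distinct names.
- Appendix 4: 40 strong P-glycoprotein inhibitors, and 18 entries in the strong CYP3A inhibitor and inducer table.
- Appendix 5: 54 drugs.

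**Appendix 3 against Appendix 4**

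| Drug | Appendix 3 table | Appendix 4 table |
|---|---|---|
| Carvedilol | P-glycoprotein substrates | Strong P-glycoprotein inhibitors |
| Methadone | CYP3A4 substrates | Strong P-glycoprotein inhibitors |
| Progesterone | CYP3A4 substrates | Strong P-glycoprotein inhibitors |
| Reserpine | CYP3A4 substrates | Strong P-glycoprotein inhibitors |

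Four names overlap: 4/87 = 4.6% of the distinct names in Appendix 3, and 4/40 = 10.0% of the prohibited P-glycoprotein inhibitor entries. No Appendix 3 name is in the CYP3A table of Appendix 4, so the breach of the heading is confined to its P-glycoprotein clause.

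**Appendix 3 against Appendix 5**

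Five names overlap, all from the CYP3A4 table: haloperidol, pimozide, quetiapine, quinine and salmeterol (5/54 = 9.3% of Appendix 5). No name is in all three appendices.

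**Close spellings**

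The near matches (nifedipine and felodipine, sitagliptin and linagliptin, quinine and quinidine) are different drugs, so the counts stand at four and five.

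**What each overlap means**

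- The four Appendix 4 names contradict the Appendix 3 heading directly. That heading also settles which list should govern: Appendix 3 was meant to exclude strong P-glycoprotein inhibitors, so the names belong only in Appendix 4.
- The five Appendix 5 names contradict nothing. The heading does not mention QT drugs, and a drug can be both a CYP3A4 substrate and QT-prolonging. The natural reading is that the unqualified ban in Section 6.9 and criterion 7 applies, but no sentence says so.
- Amendment 2 dealt with this kind of conflict for progesterone-containing products, yet the current Appendix 3 still prints progesterone. The Section 6.9 note covers contraceptives only, and the amendment's rationale does not name carvedilol, methadone or reserpine. The conflict lies wholly within current text; it is not a difference between the amendment log and the body.

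**After correction**

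87 − 4 = 83 distinct names remain in Appendix 3, with no overlap with Appendix 4, so the list matches its heading.

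**The case against.** The strongest reply is that the protocol already resolves the conflict. Section 6.9 bans strong P-glycoprotein inhibitors without qualification, exclusion criterion 8 does so at entry, and the heading makes Appendix 3 subordinate to both. Section 6.8.2 describes Appendix 3 only as a list of substrates. Its wording about all drugs not being prohibited can even be read as meaning that not all of them are. On this view, four stray names remain in a reference table and there are no competing rules.

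Much of this stands. A careful reader would apply the ban, and for progesterone-containing contraceptives the ban is explicit in inclusion criterion 8 and Section 6.9. It does not remove the error. Section 6.8.2 sets the condition of necessity and monitoring and then points to Appendix 3 with no exception, so a site could fairly use that appendix as its list of usable, monitored drugs. Four of its entries would mislead such a site.

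The safety argument is also limited, and this part of the objection stands in full:

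- None of the four drugs is in Appendix 5, and the documents give no exposure or QT data for any of them with lefamulin.
- Section 1.5.1 reports a moderate interaction between oral ketoconazole and lefamulin, but expects no interaction with potent CYP3A and P-glycoprotein inhibitors that would justify a dose adjustment. Ketoconazole is in both parts of Appendix 4, so that result cannot be attributed to P-glycoprotein alone.
- Triplicate ECGs (Section 6.4) and the QTcF stopping rules (Section 6.18.3) apply to every subject.

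There is no analytic consequence. Criteria 7 and 8 are not among the exclusion criteria that SAP Section 5.6 lists for removing subjects from the Clinically Evaluable sets (1, 3, 4, 5, 6 and 16). In SAP Section 6.1, the only concomitant medication that enters the early clinical response definition is an antibiotic for the pneumonia. The five QT names alone would not merit a comment.

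**Conclusion.** The concern holds, as a minor point. Carvedilol, methadone, progesterone and reserpine are wrongly printed in Appendix 3, against its own heading, Appendix 4, Section 6.9 and exclusion criterion 8. The count of four is exact and rests only on the printed lists, with no outside assumption. The percentages describe lists, not subjects or exposures. The documents do not say how often these drugs would be used, so the number of subjects affected cannot be estimated; the safeguards in place suggest that the harm would be small. The five Appendix 5 names need clarification only.

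**What to change.** Delete carvedilol, methadone, progesterone and reserpine from Appendix 3. Add one sentence to Section 6.8.2: *Section 6.9, exclusion criteria 7 and 8, and Appendices 4 and 5 take precedence over Appendix 3.* That sentence also settles the five QT drugs, and any QT-prolonging drug that the non-exhaustive Appendix 5 does not name, so removing or footnoting those five is optional. Notify sites of the change.

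The cost is a short protocol amendment (four deletions and one sentence) and a site notice. Data collection, sample size and analysis do not change.
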